1.1.3.3. Exploratory Objectives

The exploratory objectives include the following:

- To describe the efficacy of VGX-3100, administered alone or in combination with imiquimod, at Week 74 and/or Week 96 as measured by reduction in the surface area of the qualifying vulvar lesion(s), in subjects without a complete lesion resolution at Week 48
- To describe the long term efficacy of VGX-3100, alone or in combination with prior imiquimod, as measured by histologic regression of vulvar HSIL
- To describe the long term efficacy of VGX-3100, alone or in combination with prior imiquimod, as measured by virologic clearance of HPV-16/18
- To evaluate tissue immune responses to VGX-3100, and VGX-3100 with imiquimod, as measured in vulvar tissue samples
- To describe virologic clearance of HPV-16/18 from non-vulvar anatomic locations
- To describe association of microRNA (miRNA) profile, previous vulvoscopy, and HPV testing results with Week 48 histologic regression
- To describe patient reported outcomes (PRO) for subjects treated with VGX-3100 and VGX-3100 with imiquimod
- To describe the humoral and cellular immune response of VGX-3100 administered alone or in combination with imiquimod, post dose 3, post dose 4, and after additional dosing
- To determine the long term efficacy of VGX-3100 alone or in combination with imiquimod with respect to histopathologic regression of vulvar HSIL or virologic clearance of HPV-16/18 in vulvar tissue

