Subjects in Subgroups C and D may receive a fifth and possibly a sixth dose at Week 52 and Week 78, respectively.

To assess quality of life and related impacts on subjects, PRO instruments will be provided and will include the Short Form Health Survey version 2 (SF-36v2TM), the EQ-5D-5L (EuroQol Research Foundation), WOMAN-PRO (WOMen with vulvAr Neoplasia) Clinical Trial Version 2.0, and 2 additional PRO questions assessing quality of life after surgery or biopsy.

The total duration of the study is up to 10 weeks for the screening period and up to100 weeks for the treatment and follow-up periods. The study duration is reduced to 78 weeks for subjects that have not already completed the Week 78 visit.

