1.2.4. Study Procedures

The schedule of assessments, as outlined in the study protocol, is provided in Table 1-1.

| Tests and Observations | Screening (-10 wk to-1d) | Day 0 | 8-14 days post dose 1 Phone Call | Week 4 (± 7 days) | 8-14 days post dose 2 Phone Call | Week 12 (± 7 days) | Week 15 (± 7 days) | Week 24 (± 7 days) | Week 27 (± 7 days) | Week 38 (± 7 days) Phone Call | Week 48 (± 7 days) | Week 52 (± 14 days) | Week 74 (±14 days) | Week 78 (± 14 days) | Week 96 (± 14 days) | Week 100 (± 14 days) |
|---------------------------------------------------|-----------------------------|-----------------------|-------------------------------------|-------------------|-------------------------------------|--------------------|--------------------|--------------------|--------------------|----------------------------------|--------------------|---------------------|--------------------|---------------------|---------------------|----------------------|
| Informed consent | Х | | | | | | | | | | | | | | | |
| Medical History/Demographics | Х | | | | | | | | | | | | | | | |
| Medications (prior/concomitant) | Х | Х | Х | Х | Х | Х | Х | Х | Х | Х | Х | Х | Х | Х | Х | Х |
| Socio-behavioral assessment* | Х | | | | | | | | | | Х | | | | | Х |
| Inclusion/Exclusion criteria | Х | Х | | | | | | | | | | | | | | |
| Randomization | | Х | | | | | | | | | | | | | | |
| Physical exam (PE)/assessment ¹ | Х | Х | | Х | | Х | | Х | Х | | Х | Х | Х | Х | Х | Х |
| Vital signs | X ² | Х | | Х | | Х | | Х | Х | | Х | Х | Х | Х | Х | Х |
| Screening safety (12 lead ECG, labs) ³ | Х | | | | | | | | | | | | | | | |
| Pregnancy Testing ⁴ | Х | Х | | Х | | Х | | Х | Х | | Х | Х | Х | Х | Х | Х |
| HIV Ab by ELISA | Х | | | | | | | | | | | | | | | |
| Blood immunologic samples | X ⁵ | X ⁵ | | | | | X ⁵ | | X ⁶ | | X ⁵ | | X ⁵ | | X ⁵ | |
| OP rinse, vaginal, and intra-anal swabs | | X | | | | | | | X | | X | | X | | X | |
| Vulvar swabs | | Х | | Х | | Х | | | Х | | Х | | Х | | Х | |

CONFIDENTIAL

Inovio Pharmaceuticals, Inc. Statistical Analysis Plan, Protocol HPV-201 22 March 2021, Final Version 2.0

| | creening 10 wk to-1d) | ay 0 | 14 days post dose 1 hone Call | 'eek 4 (± 7 days) | 14 days post dose 2 hone Call | 'eek 12 (± 7 days) | 'eek 15 (± 7 days) | 'eek 24 (± 7 days) | 'eek 27 (± 7 days) | 'eek 38 (± 7 days) hone Call | 'eek 48 (± 7 days) | 'eek 52 (± 14 days) | 'eek 74 (±14 days) | 'eek 78 (± 14 days) | 'eek 96 (± 14 days) | 'eek 100 (± 14 days) |

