|-----------------------------------------------------------------------|--------------------------|------|----------------------------------|-------------------|----------------------------------|--------------------|--------------------|--------------------|--------------------|---------------------------------|--------------------|---------------------|--------------------|---------------------|---------------------|----------------------|
| Tests and Observations | S . | D | -8 P | M | ~ [] | 5 | 5 | М | 5 | W PI | 5 | 5 | \$ | 5 | M | 5 |
| Cervical colposcopy ⁷ | | Х | | | | | | | | | | | | | Х | |
| Cervical cytology, ThinPrep® ⁸ | | Х | | | | Х | | | | | Х | | | | Х | |
| Vulvoscopy ⁹ | Х | Х | | Х | | Х | | | Х | | Х | | Х | | Х | |
| Vulvar lesion standardized photography ¹⁰ | Х | Х | | Х | | Х | | | X | | Х | | Х | | Х | |
| Biopsy ¹¹ | Х | | | | | | | | | | Х | | Х | | Х | |
| Vulvar HPV genotyping ¹² | Х | | | | | | | | | | Х | | Х | | Х | |
| Inject VGX-3100 +EP ^{12, 13} | | Х | | Х | | Х | | Х | | | | X ¹³ | | X ¹³ | | |
| Post treatment reaction assessment | | X | | Х | | Х | | Х | | | | X | | Х | | |
| Dispense imiquimod + distribute imiquimod dosing log ¹⁴ | | X | | Х | | Х | | | | | | | | | | |
| Review imiquimod dosing log and usage | | | | Х | | Х | | X | | | | | | | | |
| Distribute Participant Diary (PD) | | Χ | | Х | | Х | | Х | | | | Х | | Х | | |
| Review PD ¹⁵ | | | Х | | Х | | Х | | Х | | | | Х | | Х | |
| Adverse Events | Х | Х | Х | Х | Х | Х | Х | Х | Х | Х | Х | Х | Х | Х | Х | Х |
| Patient Reported Outcomes (PROs) ¹⁶ | | X | Х | Х | X | Х | X | X | X | | X | X | X | | Х | x |

* Subjects completing the study before Week 100 will have the final socio-behavioral assessment done at their final discharge visit. This may be obtained by phone.

- ¹ Full PE mandatory at screening and study discharge (Week 100 for subjects completing this visit before Amendment 5.0), otherwise targeted PE as determined by the Investigator or per subject complaints unless signs or symptoms dictate the need for a full PE. PE will not be conducted on subjects completing the study with a Week 78 phone call.
- ² Screening vital signs must include a measured height and calculated BMI (Bodyweight in kilograms divided by height in meters squared). Weight will be measured at all dosing visits. Vital signs will not be collected on subjects completing the study with a Week 78 phone call.

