- ¹³ Potential dosing, post-treatment assessment, and distribution of the Participant Diary at Week 52 and Week 78 is applicable for partial responders only. Partial responders who reach Week 78 after Amendment 5.0 will not be offered a 6th dose.
- ¹⁴ Subjects will take home imiquimod plus an imiquimod dosing log to document their use of imiquimod. Administration of imiquimod begins on Day 0.
- ¹⁵ A phone call will be used to review the Participant Diary (PD) with subject within 8-14 days following dose 1 and 2. The patient will be expected to bring the PD to the next visit for review.
- ¹⁶ PRO measures (SF-36v2TM, EQ-5D-5L, WOMAN-PRO) plus 2 additional questions will be assessed as described in protocol Section 6.8.

- 1.2.5. Efficacy, Immunology, and Safety Parameters
- 1.2.5.1. Efficacy Parameters

The primary efficacy endpoint is the combined response outcome of histopathologic regression of vulvar HSIL and virologic clearance of HPV-16/18 in vulvar tissue at Week 48.

The secondary efficacy endpoints include the following:

- Histopathological regression is defined as no histologic evidence of vulvar HSIL at Week 48.
- Virologic clearance is defined as no evidence of HPV-16/18 at Week 48 in vulvar tissue samples.
- Proportion of subjects with no histologic evidence of vulvar HSIL or no evidence of HPV-16/18 at Week 48 in vulvar tissue samples (i.e. collected via biopsy or excisional treatment).
- Proportion of subjects with no evidence of vulvar HSIL, no evidence of vulvar LSIL (VIN1), and no evidence of condyloma on histology (i.e. biopsies or excisional treatment) at the Week 48 visit.
- Proportion of subjects with no progression of vulvar HSIL to vulvar cancer from baseline to Week 48 visit.
- Percent reduction in the cumulative surface area of qualifying acetowhite vulvar lesion(s) as determined by the quantitative analysis of standardized pre-biopsy photographic imaging of qualifying lesion(s) at Week 48 compared to baseline. Results will be classified as:
 - No clinically significant lesion resolution (reduction in lesion area of 0-25%),
 - Partial lesion area resolution (>25% and <100% reduction),
 - Complete lesion resolution (no visible lesion).

Exploratory efficacy endpoints include the following:

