1.2.5.2. Immunology Parameters

The secondary immunology endpoint is the Flow Cytometry response magnitudes at baseline and Week 27 visits.

Exploratory immunology endpoints include the following:

- Assessment of pro-inflammatory and immunosuppressive elements in vulvar tissue, which may include visualization of PD-L1, Granulysin, perforin, CD137, CD103, and possibly other relevant markers.
- Levels of serum anti-HPV-16 and antiHPV-18 antibody concentrations at baseline, Weeks 15, 27, 48, 74, and 96 visits.
- Interferon-γ ELISpot response magnitudes at baseline and Weeks 15, 27, 48, 74 and 96 visits.
- Immunohistochemistry biomarker results including but not limited to, CD8+ and FoxP3+ infiltrating cells as well as assessment of cell death via Cleaved Caspase 3 assessment.

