3.8. Subpopulations

Certain subgroups will be analyzed separately at additional time points for effectiveness of additional doses and/or surgical treatments.

- Subgroups A and B Subjects with no HSIL at Week 48 will receive 4 doses.
- Subgroups C and D Subjects with HSIL at Week 48, who have a reduction in lesion size or no increase in lesion size from baseline, may receive a fifth dose of VGX-3100 administered IM with EP at Week 52 per the judgment of the Investigator. Subjects with HSIL at Week 74 may receive a sixth dose of VGX-3100 administered IM with EP at Week 78 per the judgment of the Investigator.
- Subgroup E Subjects may receive surgical treatment per the judgment of the Investigator.

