4.3.4. Immunology Endpoints

The following immunology endpoints will be presented in tabulations:

- ELISpot results will be presented by treatment group and scheduled visit, and increase from baseline will be analyzed using an exact non-parametric 95% CI on the median at each time point after baseline (Weeks 15, 27, 48, 74, and 96).
- HPV-16 and HPV-18 E7 specific ELISA results will be presented by treatment group and scheduled visit and analyzed using an exact non-parametric 95% CI on the median at each time point after baseline (Weeks 15, 27, 48, 74, and 96).
- Increase from baseline in frequency of VGX-3100 specific CD8+/CD137+ PBMCs that are Perforin+ will be presented by treatment group and will be analyzed using an exact non-parametric 95% CI on the median.
- Change from baseline in pro-inflammatory and immunosuppressive elements in vulvar tissue, which may include visualization of PD-L1, Granulysin, perforin, CD137, CD103, and possibly other relevant markers, will be presented by treatment group and will be analyzed using a t-distribution based 95% CI on the mean.

All immunology data will be presented by study visit in data listings.

| Table 14.2.4.1A | ELISpot Results by Treatment Group and Scheduled Visit (mITT Population) |
|-----------------|---------------------------------------------------------------------------------------------------------------------------------------------------------|
| Table 14.2.4.1B | ELISpot Results by Treatment Group and Scheduled Visit (PP Population) |
| Table 14.2.4.2A | HPV-16 and HPV-18 E7 Specific ELISA Results by Treatment Group and Scheduled Visit (mITT Population) |
| Table 14.2.4.2B | HPV-16 and HPV-18 E7 Specific ELISA Results by Treatment Group and Scheduled Visit (PP Population) |
| Table 14.2.4.3A | Increase from Baseline in Frequency of VGX-3100 Specific CD8+/CD137+ PBMCs that are Perforin+ by Treatment Group (mITT Population) |
| Table 14.2.4.3B | Increase from Baseline in Frequency of VGX-3100 Specific CD8+/CD137+ PBMCs that are Perforin+ by Treatment Group (PP Population) |
| Table 14.2.4.4A | Change from Baseline in Pro-inflammatory and Immunosuppressive Elements in Vulvar Tissue by Treatment Group and Scheduled Visit (mITT Population) |

| Table 14.2.4.4B | Change from Baseline in Pro-inflammatory and Immunosuppressive | |
|-------------------|----------------------------------------------------------------------|--|

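### Exploratory ELISpot and ELISA results at Weeks 74 and 96 are not split by doses received, so they cannot isolate a response to added doses

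*SAP*

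**What the plan says.** Section 1.1.3.3 sets an exploratory objective to describe humoral and cellular responses "post dose 3, post dose 4, and after additional dosing". Section 1.2.5.2 gives the matching endpoint as "Interferon-γ ELISpot response magnitudes at baseline and Weeks 15, 27, 48, 74 and 96 visits", and lists antibody concentrations at the same visits.

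Section 4.3.4 tabulates ELISpot and ELISA by treatment group and scheduled visit. For ELISpot, "increase from baseline will be analyzed using an exact non-parametric 95% CI on the median at each time point after baseline"; for ELISA, the same kind of interval is placed on the median at each visit. Section 3.4 fixes baseline as the last measurement before the first administration of study drug.

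Added doses are optional and go to a selected group. Section 1.2.1 says that Subgroups C and D "may receive a fifth and possibly a sixth dose at Week 52 and Week 78, respectively". Section 3.8 repeats that these subjects "may receive a fifth dose of VGX-3100 administered IM with EP at Week 52". The footnotes to Table 1-1 say that dosing "at Week 52 and Week 78 is applicable for partial responders only", and that partial responders reaching Week 78 after Amendment 5.0 are not offered a sixth dose.

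For efficacy, section 4.3.2 stratifies the Week 74 and Week 96 results by number of doses received. Section 4.3.4 has no such split.

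**The concern.** The objective is organised by dose; the analysis is organised by visit. Up to Week 48 the two coincide on the planned schedule, because everyone is due the same four doses. From Week 52 they part: some subjects get a fifth dose and some do not, yet the Week 74 and Week 96 summaries hold them together.

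Three misreadings are possible:
- **Dilution.** A Week 74 median over all subjects in an arm mixes those dosed at Week 52 with those last dosed at Week 24.
- **False credit.** A Week 74 increase over the pre-dose-1 value could be put down to dose 5 when it only persists from doses 1 to 4. Splitting by dose number does not cure this; a later reference visit is needed.
- **False deficit.** A Week 74 value below the Week 27 value could be taken as no gain from dose 5 when it may reflect only the longer time since dosing.

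At stake is whether the trial can describe the immune response after additional dosing, which it names as an objective.

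**Working it through.** **Inputs.** The "Inject VGX-3100 +EP" row of Table 1-1 gives Day 0 and Weeks 4, 12 and 24, with possible doses at Weeks 52 and 78. The "Blood immunologic samples" row gives Screening, Day 0 and Weeks 15, 27, 48, 74 and 96. The visit windows are ±7 days up to Week 48 and ±14 days from Week 52. The SAP states no interval since dosing, so there is no planned figure to reproduce.

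**Step 1: weeks since last dose.** Sampling week minus week of last dose; the range adds or subtracts both visit windows.

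| Sample | Last dose | Weeks since dose | Range |
|---|---|---|---|
| Week 15 | 3 (Week 12) | 15 − 12 = 3 | 1–5 |
| Week 27 | 4 (Week 24) | 27 − 24 = 3 | 1–5 |
| Week 48 | 4 (Week 24) | 48 − 24 = 24 | 22–26 |
| Week 74 | 4 (Week 24) | 74 − 24 = 50 | 47–53 |
| Week 74 | 5 (Week 52) | 74 − 52 = 22 | 18–26 |
| Week 96 | 4 (Week 24) | 96 − 24 = 72 | 69–75 |
| Week 96 | 5 (Week 52) | 96 − 52 = 44 | 40–48 |
| Week 96 | 6 (Week 78) | 96 − 78 = 18 | 14–22 |

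The pooled Week 74 summary therefore spans a gap of 50 − 22 = 28 weeks between its two dose groups. At Week 96 the spread is up to 72 − 18 = 54 weeks.

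**Step 2: which visits are comparable.** No blood is scheduled soon after dose 5 or 6. Week 74 after dose 5 (22 weeks) is 19 weeks further from dosing than Week 27 after dose 4 (3 weeks), but only 2 weeks closer than Week 48 after dose 4 (24 weeks). Week 48 also precedes dose 5. It is therefore the near-matched reference already in the table.

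**Step 3: illustration of size.** The SAP gives no rate of waning, so the half-life h is an assumption. Suppose equal peaks after each dose and exponential decline. The expected ratio of two readings is then 2^(−d/h), where d is the extra weeks since dosing in the first.

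| h (weeks) | Week 74: 4 doses / 5 doses (d = 28) | Week 74 after dose 5 / Week 27 (d = 19) | Week 74 after dose 5 / Week 48 (d = −2) | Week 96 after dose 6 / Week 74 after dose 5 (d = −4) |
|---|---|---|---|---|
| 6 | 0.04 | 0.11 | 1.26 | 1.59 |
| 12 | 0.20 | 0.33 | 1.12 | 1.26 |
| 26 | 0.47 | 0.60 | 1.05 | 1.11 |
| 104 | 0.83 | 0.88 | 1.01 | 1.03 |
| no waning | 1.00 | 1.00 | 1.00 | 1.00 |

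The distortion against Week 27 runs from severe to none, depending wholly on h. Against Week 48 it is small unless waning is fast, and it slightly favours dose 5. A sixth-dose contrast from Week 74 to Week 96 is itself mismatched (22 against 18 weeks).

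**Step 4: smallest group for an exact interval.** The widest exact interval on a median runs from the smallest to the largest value and has coverage 1 − 2 × 0.5^n. For n = 5 this is 93.75%; for n = 6 it is 96.875%. A two-sided 95% interval therefore needs at least 6 subjects.

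**The case against.** The strongest reply is that section 4.3.4 makes no faulty comparison. It gives separate summaries at each visit, with no contrast between visits or dose numbers and no estimate of a benefit from dose 5. The objective is exploratory and only descriptive, and the sampling times are a design choice rather than an error of analysis. Listings carry relative study days (sections 3.2 and 3.11) and dosing is listed (section 4.4.1), so time since last dose can be recovered for each subject.

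Much of this stands. A reader might infer that the by-visit table sets near-dose against late values and will understate the response to added doses. The SAP does not support that: it plans no such contrast, it documents no waning, and the near-matched Week 48 result is in the same table. Against Week 48, timing leans slightly towards dose 5. A reader might also extend the point to all cellular responses, but the flow cytometry endpoint is set at baseline and Week 27 only, before any added dose.

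The reply leaves one thing unanswered. The plan names the response after additional dosing as something to describe, and no quantity in section 4.3.4 describes it. Listings let a reader rebuild it, but they do not define it in advance. Section 4.3.2 already applies the dose split to efficacy.

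**Conclusion.** The point holds as a minor improvement to the exploratory ELISpot and ELISA summaries. Two parts need no assumption about kinetics: the Week 74 and Week 96 summaries pool subjects by visit whatever their dose count (50 against 22 weeks since last dose at Week 74), and an increase over the pre-dose-1 baseline cannot tell a response to dose 5 from persistence after doses 1 to 4. The third part is conditional: added doses may look weaker if Week 74 or 96 is read against Week 15 or 27 and if responses wane. With an assumed half-life of 12 weeks, an equal response to dose 5 would read 33% of the Week 27 value (11% at 6 weeks, 60% at 26, 88% at 104, 100% with no waning). The direction is not fixed, since false credit to dose 5 is also possible.

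No primary, secondary or safety analysis is touched. The data at issue are few: added doses go only to partial responders in a trial of about 36 subjects, no sixth dose is offered after Amendment 5.0, and section 1.2.1 shortens the study to 78 weeks for subjects who had not completed that visit.

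**What to change.** In section 4.3.4:

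1. Present ELISpot and ELISA at Weeks 74 and 96 by number of doses received within treatment group, as section 4.3.2 does for efficacy.
2. Show weeks since last dose for each visit and dose group, and state that Week 74 and 96 values are not to be read against Weeks 15 and 27 as a measure of the added doses.
3. Define the fifth-dose response as the within-subject change from Week 48 (24 weeks after dose 4) to Week 74 (22 weeks after dose 5) in subjects given dose 5. Report the median with an exact 95% interval where n is at least 6, and list the values otherwise.
4. List sixth-dose data only, with a note that Weeks 74 and 96 differ in time since last dose (22 against 18 weeks).

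The cost is SAP wording and one derived variable, from samples already scheduled. The downside is small numbers in the 5- and 6-dose groups; in the 12-subject imiquimod arm the interval may not be obtainable. The within-subject change also has no concurrent control and describes a late response only, so it should be reported as descriptive.

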1. INFORMATION FROM THE STUDY PROTOCOL

1.1. Introduction and Objectives

1.1.1. Introduction

Human papillomaviruses (HPV) are double-stranded deoxyribonucleic acid (DNA) viruses with more than 100 genotypes, some of which can lead to malignant neoplasia, localized primarily in the anogenital area and aerodigestive tract, in both men and women. HPV-16/18 is involved in about 83% of HPV-associated vulvar high grade squamous intraepithelial lesion (HSIL) cases in the U.S. [1] and about 72% in Europe [2]. Persistent infection with 1 or more oncogenic (high-risk) HPV genotypes can lead to the development of precancerous, histologic HSIL. Vulvar HSIL can lead to vulvar cancer with an estimated 6,020 new cases and 1,150 attributable deaths annually for year 2017 in the United States [3] and about 9,776 new cases in 2015 in Europe [4]. Vulvar cancers consist largely of squamous cell carcinomas and accounts for approximately 5% of all female genital malignancies [5].

HPV-associated vulvar intraepithelial neoplasia (VIN) is a chronic (typically persisting for years), premalignant disorder of the vulvar skin that is caused by persistent infection with 1 or more high-risk genotypes of HPV. Infected cells produce E6 and E7 oncoproteins constitutively, which increases the degradation of cell cycle regulation proteins p53 and pRb, respectively, resulting in unrestricted cell growth and neoplasia. The basis for progression to cancer is, therefore, attributed to the viral proteins E6 and E7. VGX-3100 specifically induces immune responses against E6 and E7, thereby enabling clearance of pre-malignant cells as demonstrated in the Phase 2 study of cervical HSIL [6].

Vulvar HSIL remains a significantly under met medical condition for the following reasons which will be described further: 1) the rate of recurrence of vulvar HSIL under currently used surgical and medical approaches is extremely high, 2) there is a high psychological and physical negative impact of surgery, 3) vulvar HSIL is symptomatic and impacts activities of daily living, 4) prophylactic HPV vaccines have no therapeutic activity against vulvar HSIL and have not achieved universal uptake, leaving a population of susceptible and impacted women, and 5) the early diagnosis of vulvar HSIL is limited to visual inspection with biopsy.

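### SAP 4.3.4 puts the ELISA confidence interval on the post-baseline median level, not on the increase from baseline, so it does not by itself estimate a humoral response to VGX-3100

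*SAP*

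**What the plan says.** The objective is exploratory (SAP 1.1.3.3): "To describe the humoral and cellular immune response of VGX-3100 administered alone or in combination with imiquimod", after doses 3 and 4 and after any further dosing. The matching endpoint in 1.2.5.2 is "Levels of serum anti-HPV-16 and antiHPV-18 antibody concentrations at baseline, Weeks 15, 27, 48, 74, and 96 visits".

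Section 4.3.4 then gives four analysis bullets:

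- **ELISpot:** "increase from baseline will be analyzed using an exact non-parametric 95% CI on the median at each time point after baseline".
- **ELISA:** "HPV-16 and HPV-18 E7 specific ELISA results will be presented by treatment group and scheduled visit and analyzed using an exact non-parametric" interval (95%) for the median level at each of Weeks 15, 27, 48, 74 and 96. No increase or change is named.
- **Flow cytometry:** "Increase from baseline in frequency of VGX-3100 specific CD8+/CD137+ PBMCs that are Perforin+ will be presented by treatment group".
- **Tissue markers:** "Change from baseline in pro-inflammatory and immunosuppressive elements in vulvar tissue".

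The titles of Tables 14.2.4.2A and B refer to ELISA results by arm and visit, also without change. Section 3.4 defines baseline as the last value before the first dose. Footnote 5 of Table 1-1 requires serum before that dose.

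**The concern.** A CI on a post-baseline level contains no baseline term, so no value of it means that there was no response. That matters here for two reasons. First, every subject enters with HSIL that is positive for HPV-16, HPV-18 or both (1.2.1), and the Introduction notes "Infected cells produce E6 and E7 oncoproteins constitutively". Some anti-E7 antibody before dose 1 is therefore plausible. Second, both randomised arms receive VGX-3100, so no untreated arm can separate antibody due to infection from antibody due to the vaccine. Each subject's own baseline is the only internal reference, and the stated inference does not use it.

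At stake is how clearly the humoral objective can be answered. The level CI carries all of the between-subject spread, which a paired comparison removes, and the arms are small. The primary conclusion is not touched.

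**Working it through.** **Text check.** Three of the four bullets in 4.3.4 name an increase or change; ELISA does not. The endpoint wording does not explain this. Section 1.2.5.2 words ELISpot in the same way as antibody, as values at baseline and the same later visits, yet 4.3.4 analyses ELISpot as an increase. Where the SAP wants both score and change it says so, as in 4.3.3 for SF-36, EQ-5D-5L and WOMAN-PRO. The SAP states no figure on this point that could be reproduced.

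**Arm sizes.** 1.2.1 gives 24 and 12 subjects, and 3.1 assumes that 90% are evaluable at Week 48: 24 × 0.9 = 21.6 and 12 × 0.9 = 10.8, taken as 22 and 11.

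**Exact CI for a median.** The order-statistic interval uses ranks 2 to 10 at n=11 (coverage 98.8%) and ranks 6 to 17 at n=22 (98.3%).

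**Assumptions, not from the SAP.** Titres are log-normal. The between-subject ln-SD is 1.2 or 0.8 and the within-subject ln-SD is 0.4 or 0.6. The true effect is a doubling, ln 2 = 0.693.

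**Paired CI.** The SD of a within-subject difference is √2 × within-SD. Its lower limit exceeds zero (fold-rise above 1) when at least 10 of 11, or 17 of 22, subjects show a rise.

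- Within-SD 0.4: the SD of the difference is 0.566, and P(rise) = Φ(0.693/0.566) = Φ(1.225) = 0.890. Then P(at least 10 of 11) = 65.4% and P(at least 17 of 22) = 97.2%.
- Within-SD 0.6: the SD is 0.849, and P(rise) = Φ(0.817) = 0.793. The results are 30.2% and 70.4%.

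**Level CI.** The SAP sets no rule for reading a response from it. A lenient reading is that its lower limit lies above the observed baseline median. This was simulated, with subject-level correlation induced by the two SDs.

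| ln-SD between / within | n | Paired CI excludes no rise | Level CI above baseline median |
|---|---|---|---|
| 1.2 / 0.4 | 11 | 65% | 11% |
| 1.2 / 0.4 | 22 | 97% | 34% |
| 1.2 / 0.6 | 11 | 30% | 11% |
| 1.2 / 0.6 | 22 | 70% | 30% |
| 0.8 / 0.6 | 11 | 30% | 23% |
| 0.8 / 0.6 | 22 | 70% | about 55% |

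**Width at 1.2 / 0.4.** The level CI spans about 14-fold (n=11) and 5-fold (n=22). The paired fold-rise CI spans 3.3-fold and 2.1-fold.

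**Larger rises at 1.2 / 0.4, level CI.** A 4-fold rise is seen in 57% (n=11) and 94% (n=22) of trials, and an 8-fold rise in 89% and 99.9%.

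**The case against.** A reader might infer that the planned analysis cannot show a humoral response at all. The documents do not support that. Baseline is part of the endpoint, results are presented by visit, and Listing 16.2.6.8A holds every value. A rise can be read, and the figures for 4-fold and 8-fold rises show that a large one usually would be in the larger arm. What is missing is a paired estimate with its CI. One could make the level analysis look worse by requiring separate baseline and post-dose CIs not to overlap, but the SAP plans no such rule.

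A reader might also infer that infection alone would push the CI away from zero. The SAP gives no anti-E7 seroprevalence: it says that infected cells make E7, not that these women have antibody to it. Counting seronegatives as zero, the CI clears zero only if at least 10 of 11 or 17 of 22 are seropositive. At 50% seroprevalence the probability is under 1% in either arm; at 70% it is 11% and 31%. Exposure is also type-specific, since eligibility requires HPV-16 or HPV-18, not both.

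Three further points stand. The 1.2 / 0.4 case favours pairing, because it implies a baseline-to-post correlation of 1.44/(1.44 + 0.16) = 0.90; at 0.8 / 0.6 it is 0.64/(0.64 + 0.36) = 0.64 and the gain is modest. The SAP omits the change without ruling it out, and the table shells are in a separate document (7.2), so a change column may exist there. The endpoint is exploratory, and 3.2 confines formal testing to the primary endpoint.

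None of this explains why ELISA alone is analysed as a level.

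**Conclusion.** The point holds in limited form. The ELISA bullet differs from its three neighbours without a stated reason. Its CI does not by itself estimate a response to VGX-3100 and is imprecise for modest rises. The inconsistency is certain from the text; the size of the loss is not, because every titre SD used here is assumed. Over the cases tabulated, the chance of showing a doubling is higher with the paired CI by between 7 and 54 percentage points at n=11 (30 less 23, 65 less 11) and between about 15 and 63 at n=22 (70 less 55, 97 less 34). Pre-existing anti-E7 antibody is plausible but not documented. This is a minor, easily corrected weakness in an exploratory analysis.

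**What to change.** In the ELISA bullet of 4.3.4 and in Tables 14.2.4.2A and B, add the within-subject increase from baseline for HPV-16 E7 and HPV-18 E7 separately. Give the exact non-parametric 95% CI on its median at Weeks 15, 27, 48, 74 and 96. Either a difference, which matches ELISpot, or a fold-rise would serve; name one in advance. Keep the levels, including baseline, as descriptive rows.

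The cost is one sentence and one derived variable, with no new samples. The small downside is that values below the assay limit need a handling rule fixed beforehand. A fold-rise is sensitive to that rule if many baselines are below the limit, which is a further reason to keep the levels on display. Make the change before the titres are seen.
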